Open-label, single dose given daily for 6 days in healthy volunteers. A single cohort will enroll 14 subjects (7M/7F) of which 4 will be backups (2M/2F), so that at least 8 subjects (4M/4F) complete the protocol procedures. Subjects will follow a diet low in soy isoflavones for 7 days before treatment, during the 6 days of treatment and 7 days after treatment. Subjects will fast at least 8 h before the first dose, 3rd dose and the 6th dose. The test article will be administered starting on day 1 and the dose used in this study will be determined based on safety and PK analysis from the single ascending dose study. Subjects will be administered test article daily during their schedule clinic visits. Subjects will remain in the clinic 4 hours after the first dose and 12 hours after the 6th dose for observations and blood sample collection for clinical lab assessment, PK and PD. Subjects will remain fasted for 4 hours after the test article administration on days 1 and 6. On the 6th day, subjects will be provided a standardized low soy meal after the 4-hour blood draw and after the 8-hour blood draw. Blood sampling and/or observations will be performed on dosing days 1-6 as described in the schedule of events. Subjects will return to the clinic on days 7, 8 and 13 after initial dosing for blood sampling and/or observations as detailed in the schedule of events. Subjects may not miss any clinic visits. At the conclusion of the study, data will be analyzed to determine safety and PK, and data will be analyzed from all cohorts to determine PD.

Objectives:

Primary Objectives:

- Determine the overall adverse event and PK profiles of single ascending doses of BIO 300 Oral Powder in healthy volunteers
- Determine the overall adverse event and PK profile of multiple doses of BIO 300 Oral Powder in healthy volunteers

Secondary Objectives:

- Determine the effects of single and multiple doses of BIO 300 Oral Powder on blood-based biomarkers
- Use a combination of the PK and PD profiles from the single and multiple doses of BIO 300 Oral powder to identify the putative BIO 300 Oral Powder human efficacious dose

Endpoints:

Primary

Evaluate the safety and pharmacokinetics of BIO 300 Oral Powder in Healthy Volunteers

Secondary

Characterize the expression of blood-based biomarkers

Study Population:

[figure not shown]

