- 6 subjects/cohort (3M/3F) will be recruited for the single ascending dose study, and at least 6 (3M/3F) subjects/cohort will complete all aspects of the study. 2 additional subjects (1M/1F),

[figure not shown]
will be screened, consented and available as backups for each cohort.

- 10 (5M/5F) subjects will be recruited for the multiple single dose study, and at least 8 (4M/4F) subjects will complete all aspects of the study. 4 additional subjects (2M/2F) will be screened, consented and available as backups.
- In total, at least 32 healthy volunteers who will complete all aspects of the trial.

Phase:	1
Description of Sites/Facilities Enrolling Participants:	Nucleus Network (formally Prism Clinical Research) [name]
Description of Study Intervention:	BIO 300 Oral Powder will be provided by Humanetics Corporation, Minneapolis, Minnesota. [REDACTED] [REDACTED] The inactive ingredients include povidone K12 and sucralose powder. The vials are labeled with clinical study information including the lot number, storage instructions to store at controlled room temperature 15-30°C (59-86°F) and the statement "CAUTION: New Drug, limited by Federal law to investigational use."
Study Duration:	Approximately 8 months
Participant Duration:	The duration of study participation will be 35 days for Cohorts 1 – 4 (28-day screening period; Dosing on day 1; final follow-up visit on Day 8). The duration of study participation will be 41 days for Cohort 5 (28-day screening period; Dosing on days 1 - 6; final follow-up visit on day 13)

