6.1.2 DOSING AND ADMINISTRATION

Single Ascending Dose Cohorts:

Cohort 1 dose: one BIO 300 Oral Powder sachet, 500 mg genistein

Cohort 2 dose: two BIO 300 Oral Powder sachets, 1000 mg genistein (2X the dose of Cohort 1 in the absence of dose-limiting toxicity [DLT])

Cohort 3 dose: four BIO 300 Oral Powder sachets, 2000 mg genistein (2X the dose of Cohort 2 in the absence of DLT)

Cohort 4 dose: TBD based on the observed PK and AE profiles in the first 3 dose cohorts

All single dose cohorts will be administered the drug at the clinic under the supervision of the study personnel. Subjects will follow a diet low in soy isoflavones for 7 days before and 7 days after treatment and will fast at least 8 h before dosing. Subjects will remain fasted for 4 hours after the test article

administration. Subjects will remain in the clinic 12 hours after dosing. Subjects will be provided a standardized low soy meal after the 4-hour blood draw and after the 8-hour blood draw. The purpose of fasting is to standardize the effect of food on PK and PD markers.

Multiple Single Dose Cohort:

The cohort 5 dose will be dosed daily for 6 consecutive days at the highest dose or the maximum tolerated dose from the Single Ascending Dose cohorts. Subjects will consume the test article each day within +/- 2 hours of time when the first dose was administered and not within 1 hour before or after eating. The Day 6 dose will be administered during clinic visit 7 so that PK and PD blood draws can be timed after the dose.

Drinking of room temperature water only, (up to 240 mL) will be encouraged following administration of each BIO 300 Oral Powder sachet.

Subjects will follow a diet low in soy isoflavones for 7 days before treatment, during the 6 days of treatment and 7 days after treatment. Subjects will fast at least 8 h before the first dose, 3rd dose and the 6th dose. Subjects will remain in the clinic 4 h after the first dose and 12 hours after the 6th dose. Subjects will remain fasted for 4 hours after the test article administration on days 1 and 6. On the 6th day, subjects will be provided a standardized low soy meal after the 4-hour blood draw and after the 8-hour blood draw. The purpose of fasting is to standardize the effect of food on PK and PD markers.

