7 STUDY INTERVENTION DISCONTINUATION AND PARTICIPANT DISCONTINUATION/WITHDRAWAL

7.1 STOPPING CRITERIA FOR DISCONTINUATION OF THE STUDY INTERVENTION

Discontinuation of a subject and early stopping of the study intervention will be based on the following unacceptable adverse events (AEs) and must be attributable to the investigational drug BIO 300 Oral Powder (i.e., possibly, probably or definitely related to the study drug) to constitute a Dose-Limiting Toxicity (DLT).

- Non-hematologic toxicities of Grade 3 or higher, with the following exceptions:
 - anorexia
 - fatigue
 - infection without neutropenia

- Grade 3 AST/ALT elevations ≤ 7 days
- Grade 3 or 4 electrolyte abnormalities that are corrected to Grade 2 or less in less than 48 hours.
- Occurrence of a VTE (DVT or pulmonary embolism).

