7.5 DOSE ESCALATION CRITERIA

A Safety Monitoring Committee (SMC) consisting of a Humanetics representative, the Medical Monitor and Principal Investigator, or their recognized delegates will review all available data. The determination for escalation to the next Cohort will require, at a minimum, a review of all safety data of 6 subjects in the previous SAD Cohort through at least Day 3. Decisions to proceed with dose escalations, adding additional subjects to the current Cohort, and possible dose adjustments will be made following this review with the Medical Monitor and Principal Investigator agreeing with the decision. Whether additional information such as PK or PD data may be needed before a decision to escalate can also be determined by the SMC. The primary responsibility of the SMC is to regularly monitor the overall safety of patients enrolled in the study, while protecting the scientific integrity of the study data. Dose escalation criteria will be the following:

- Dose escalation may occur if no more than 2 subjects in a 6-subject cohort experiences a dose-limiting toxicity (DLT, as defined below).
- If 3 DLTs occur (3/6 subjects), an additional 2 subjects will be treated with the same dose.
- If no additional DLTs occur (3/8 subjects), dose escalation may proceed.
- The study sponsor will temporarily cease enrollment for evaluation if in any given cohort 4/8 subjects experience DLTs attributable to BIO 300 Oral Powder as the MTD (maximum tolerated dose) will have been exceeded and no further dose escalation will occur.

DLT is any grade 3 or grade 4 adverse event listed in the draft FDA document entitled "*Toxicity Grading Scale for Healthy Adult and Adolescent Volunteers Enrolled in Preventive Vaccine Clinical Trials*."

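### The 4/8 stopping rule in protocol 7.5 covers any cohort, but its actions do not hold the remaining daily doses in cohort 5, the six-day repeat-dose cohort

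*Combined protocol and SAP*

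**What the plan says.** Protocol 7.5 sets the cohort-level rule. "The study sponsor will temporarily cease enrollment for evaluation if in any given cohort 4/8 subjects experience DLTs attributable to BIO 300 Oral Powder", the reason given being "as the MTD (maximum tolerated dose) will have been exceeded and no further dose escalation will occur". In the same section, "DLT is any grade 3 or grade 4 adverse event listed in the draft FDA document entitled" the FDA vaccine-trial toxicity scale.

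The denominator of eight comes from the single ascending dose (SAD) part, where a six-subject cohort with three DLTs is expanded by two.

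Cohort 5 is different in kind. Protocol 6.1.2 states: "The cohort 5 dose will be dosed daily for 6 consecutive days at the highest dose or the maximum tolerated dose" from the SAD cohorts. The synopsis adds that "10 (5M/5F) subjects will be recruited for the multiple single dose study", with four backups, and that "Subjects will be administered test article daily during their schedule clinic visits".

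Other provisions bear on stopping:

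- Protocol 7.1: "Discontinuation of a subject and early stopping of the study intervention will be based on the following unacceptable adverse events (AEs"). These events "must be attributable to the investigational drug BIO 300 Oral Powder (i.e., possibly, probably or definitely related to the study drug"). The section gives no cohort count and lists exceptions, including Grade 3 AST/ALT rises lasting seven days or less.
- Protocol 7.3: the investigator may withdraw an individual subject.
- SAP 6: the Safety Monitoring Committee (SMC) may recommend stopping or changing the regimen, and the sponsor makes the final decision.
- Protocol 10.1.2: the study may be suspended for reasonable cause.
- Protocol 10.1.7: the sponsor discontinues the study if, with the Medical Monitor, it judges the risk unreasonable and significant.

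**The concern.** In a single-dose cohort nothing remains to be given once the DLTs are seen, so ceasing enrolment and barring escalation is a complete response. In cohort 5 it is not. Escalation has already ended. Ceasing enrolment bars later starts, including backups, but does nothing for subjects partway through the six days, and the next dose falls due about a day later.

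The subjects are healthy volunteers with no expected benefit, in the only repeat-dose phase, at the highest dose or the MTD. At a count that the plan itself equates with exceeding the MTD, the written rule leaves the remaining subjects' doses to discretion while the evaluation runs.

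**Working it through.** **1. Does any provision hold cohort 5 doses at the trigger?**

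| Provision | Tied to a count? | Effect on cohort 5 subjects without a DLT |
|---|---|---|
| 7.5 | Yes, 4/8 | Bars new starts and escalation; silent on remaining doses |
| 7.1 | No | Stops the affected subject; a cohort-wide stop is one possible reading |
| 7.3 | No | Individual withdrawal, on the investigator's opinion |
| SAP 6 | No | SMC may recommend; its set decision points follow each SAD cohort |
| 10.1.2, 10.1.7 | No | Suspension or discontinuation, by judgement |

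None says that doses are held while a decision is pending.

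**2. How many doses are at issue?** The documents state no DLT rate and no operating characteristic for the rule, so there is no plan figure to reproduce.

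From the documents: 10 subjects, 6 daily doses (10 × 6 = 60 planned), trigger at the fourth subject with a DLT. Assumed:

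- DLT rate per course p of 10%, 20%, 30%, 37.5% (the 3/8 at which 7.5 still lets escalation proceed) or 50%;
- constant daily risk h = 1 − (1 − p)^(1/6);
- all ten start together;
- an affected subject stops from the next day;
- without the hold, everyone else is dosed to Day 6.

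Day 5 is the last day on which a trigger can save a dose. By then each subject's risk is 1 − (1 − p)^(5/6), and the chance of a trigger is the binomial probability of at least 4 of 10 at that risk. At p = 20% the risk is 1 − 0.8^(5/6) = 0.170, giving 0.0737. Expected doses come from an exact day-by-day chain; saved = doses without hold − doses with hold.

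| p | Fourth DLT by Day 5 | Fourth DLT, whole course | Doses, no hold | Doses, hold | Saved |
|---|---|---|---|---|---|
| 10% | 0.0069 | 0.0128 | 57.45 | 57.38 | 0.07 |
| 20% | 0.0737 | 0.1209 | 54.78 | 54.02 | 0.76 |
| 30% | 0.2410 | 0.3504 | 51.98 | 49.35 | 2.63 |
| 37.5% | 0.4155 | 0.5533 | 49.77 | 45.01 | 4.76 |
| 50% | 0.7096 | 0.8281 | 45.83 | 36.96 | 8.87 |

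Dividing the saving by the Day 5 probability gives the saving in a course that triggers in time: 9.8, 10.3, 10.9, 11.5 and 12.5 doses.

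**3. Sensitivity.**

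- *Staggered starts* (assumed two per day over five days, so that ceasing enrolment already bars later starts; 100,000 simulated courses): extra doses saved 0.08, 0.84, 2.76, 4.81 and 8.23.
- *Laboratory DLTs only* (assumed all found at the pre-dose Day 3 draw, with results before the Day 4 dose): risk after two doses is 1 − (1 − p)^(2/6) = 0.035, 0.072, 0.112, 0.145 and 0.206. P(at least 4 of 10) is 0.0003, 0.0039, 0.0190, 0.0448 and 0.1322. Each trigger with X affected saves (10 − X) × 3 doses, on average 0.005, 0.07, 0.33, 0.78 and 2.24.
- *Early-onset toxicity*: if exactly four DLTs have occurred after dose d, the unheld doses are (10 − 4) × (6 − d), from 30 at d = 1 to 6 at d = 5.

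**4. The count.** Four of eight, carried to ten subjects, can mean four subjects or half (five). Over the whole course P(at least 5 of 10) is 0.0016, 0.0328, 0.1503, 0.3057 and 0.6230, against the higher whole-course figures above for four. This is a secondary wording point.

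**The case against.** The strongest reply is that 7.5 is headed as dose escalation criteria, every fraction in it follows the SAD expansion from six to eight, and a denominator of eight has no meaning for a cohort of ten. On that view a single-dose rule is being faulted for lacking repeat-dose actions. The point has weight, and the rule's reach to cohort 5 is arguable. But its wording is not limited to SAD cohorts, and a SAD-only reading leaves the sole repeat-dose cohort with no count-based rule.

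The second reply is that dosing can already be stopped at any count. The Principal Investigator sits on the SMC and may withdraw subjects, every dose is given at a clinic visit, the SMC must pass on a recommendation immediately, and 7.1 can be read cohort-wide. This stands too. A reader might infer that the plan requires dosing to continue after four DLTs, or offers no way to stop it. The documents do not support that: they permit a hold without requiring one.

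It also follows that the doses-saved figures are ceilings within their model. If staff act at the fourth DLT, the saving is zero. Doses saved are not harms avoided. The larger figures need rates that look less likely, since 2.2.3 describes prior human safety as exceptional and the amendment history (10.3) shows that all four SAD cohorts were run. Neither fact settles the risk of six days' repeat dosing.

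**Conclusion.** The point holds as a gap in the written rule: the 4/8 trigger has no action that protects cohort 5 subjects still on treatment, or does not reach cohort 5 at all. It does not show that subjects would in practice be dosed on.

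The size is modest. The average saving is 0.07 of 60 doses at an assumed 10% DLT rate, 0.8 at 20% and 8.9 at 50%, and much less if DLTs appear only in laboratory results. These figures rest on assumed rates, constant daily risk, a common start and no use of the discretionary powers. Toxicity concentrated after the first doses would raise them.

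This is a cheap improvement worth considering, held with moderate confidence.

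**What to change.** Add to protocol 7.5 and SAP 6: in cohort 5, once a fourth dosed subject has a DLT as defined in 7.5 (Grade 3 or 4) that is possibly, probably or definitely related to BIO 300 Oral Powder, all further cohort 5 doses and any backup starts are held until the SMC review and the sponsor's decision are complete. The SMC and sponsor keep the power to hold earlier.

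Count subjects dosed in cohort 5, not a fraction of eight. Do not apply the 7.1 exceptions to this count. A Grade 3 AST/ALT rise first seen on Day 1 could not be shown to last beyond seven days until after Day 8, and the last dose is on Day 6. That exception could therefore keep every such rise out of the count while doses remain, although protocol 2.2.1 lists liver enzyme increases as rare but serious.

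The cost is one sentence in each document and, if triggered, one ad hoc meeting of the existing SMC. No staff, visits or samples are added. The downside is that a hold by Day 5 may lose the Day 6 PK profile, part of a primary endpoint. Under the model above, that probability is at most 0.7% at a true DLT rate of 10% or less; it rises with the rate (7.4% at 20%).

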8 STUDY ASSESSMENTS AND PROCEDURES

8.1 CRITERIA FOR EVALUATION

Safety:

The safety profile of BIO 300 Oral Powder will be based on the results of CBC with differential, coagulation parameters, serum chemistries, urinalysis, ECGs, and vital signs the reporting of adverse events.

Pharmacokinetics:

Blood samples will be collected at multiple timepoints after BIO 300 Oral Powder administration and processed for serum isolation. Serum concentrations of genistein aglycone will be measured from PK parameters (C_{max} , T_{max} , clearance, $AUC_{(0-24;0-48;0-INF)}$, volume of distribution, $T_{1/2}$ and drug accumulation index) which will be calculated using standard procedures and statistical analyses.

Pharmacodynamics:

Blood samples will be collected at multiple timepoints in PAXgene tubes after BIO 300 Oral Powder administration. It will be subjected to RNA sequencing to explore biomarkers which may be predictive of BIO 300 Oral Powder effectiveness.

8.2 SAFETY AND OTHER ASSESSMENTS

Physical Exam – Examination of the participant’s cardiovascular, HEENT, lymphatic, pulmonary, gastrointestinal, musculoskeletal, and neurological systems.

Vital Signs – Vital signs will record the patient’s height, weight and BMI. They will also measure heart rate, blood pressure (systolic and diastolic), respiratory rate, and body temperature.

Electrocardiogram – ECGs occur during the screening visit, on visit 2 (1 hr before, 1hr after, 2 hrs after and 4 hrs after BIO 300 Oral Powder dose), and visits 3-5 for the SAD phase. ECGs will occur during the screening visit, visit 2 (1 hr before, 1hr after, 2 hrs after and 4 hrs after BIO 300 Oral Powder dose), visits 3-4, visit 7 and visit 10 for the multiple single dose phase. ECGs will be digitally read locally at the study site. ECGs will be completed in triplicate and the average will be used to determine if the study subject has an abnormal reading.

QTc Interval Prolongation – Fridericia-corrected QTc (QTcF) interval from all subjects in both the SAD and the multiple single dose studies will be used to evaluate QTcF interval prolongation. QTcF prolongation will be determined by evaluating ECG at baseline (pre-dose) and at multiple time points around the predicted C_{max} of BIO 300 Oral Powder (ECG timepoints listed above). QTcF intervals will be reported for each dosing cohort as a mean and standard deviation. The upper limit for QTcF interval prolongation will be >480 ms or absolute QTcF change from baseline of >30 ms with a 95% confidence interval. The relationship between drug exposure and mean QTcF interval change will be evaluated in the SAD study using both C_{max} and AUC. Any adverse events that may signal a potential proarrhythmic effect will be carefully monitored (e.g., Torsade de pointes, sudden death, ventricular tachycardia, seizures, etc.).

Complete Blood Count – Blood sampling for the laboratory parameters will be performed during the screening and BIO 300 Oral Powder treatment period according to the study schedule (**Section 1.3**). A complete blood count with differential will evaluate hemoglobin, hematocrit, red blood cells (RBCs), white blood cells (WBCs), neutrophils, lymphocytes, monocytes, eosinophils, basophils, and platelet count.

Serum Chemistry and Fasting Lipid Panel – Blood serum will be used to evaluate the blood chemistry parameters. Serum chemistries to include total protein, albumin, sodium, potassium, chloride, bicarbonate, glucose, BUN, creatinine, alkaline phosphatase, ALT, AST, uric acid, LDH, total and direct bilirubin, phosphorous, calcium, magnesium, amylase, lipase, total cholesterol, triglycerides, HDL. Subjects will fast at least 8 h prior to blood collection for serum chemistries.

PTT/INR – Prothrombin Time (PTT) is a test that evaluates a subject’s ability to appropriately form blood clots. The International Normalized Ratio (INR) is a calculation based on results of the PTT that is used to monitor individuals who are being treated with the blood-thinning medication.

Pregnancy Test – Tests will occur at screening, day 1 and during the final visit (SAD, day 8, visit 5; Multiple Single Dose, day 13, visit 10). Tests will use urine or serum for determination of β -HCG.

Viral Testing – Test will occur at screening for both studies. Tests will utilize blood for analysis of the Hepatitis B surface antigen, Hepatitis C antibody, and HIV1 and HIV2 antibody.

Urinalysis – To include pH, specific gravity, dipstick determinations of protein, glucose, ketones and bilirubin, blood and reflex microscopic exam (reflex only if any qualitative measurements or appearance return abnormal)

Concomitant Medications – A record of concomitant medications will be collected for all subjects from the screening visit through BIO 300 Oral Powder treatment and the one-week follow-up phase.

Assessment of Adverse Events – All adverse events (AEs) will be collected from the time the subject takes their first dose of BIO 300 Oral Powder until 7 days after their last dose of BIO 300 Oral Powder. AEs will be documented and submitted to the Sponsor. Any serious AEs (SAEs) will be documented and reported to the Sponsor within 24 hours of awareness (see **Section 8.3**).

Blood-Based Biomarkers – Whole blood will be collected for biomarker analysis. Blood will be collected pre-dose, at several time points around the predicted C_{max} of BIO 300 Oral Powder. The collected samples will be subject to RNA extraction and next-generation RNA sequencing on the Illumina HiSeq platform with paired-end sequencing.

8.3 BLOOD SAMPLING FOR PHARMACOKINETICS, SAFETY AND BIOMARKERS

Blood will be collected from all subjects to monitor BIO 300 Oral Powder pharmacokinetics, safety, and biomarkers. At each visit where blood sampling occurs, whole blood and serum may be collected for pharmacokinetics, complete blood counts (CBC) with differential, serum chemistry, clotting (PT/INR, PTT) and RNA extraction. A summary of blood draws for safety and biomarkers can be found in **Section 1.3 Schedule of Activities**. Below is an overview of the details of the blood collection summarized by visit.

For blood draws, whole blood will be collected in one 3 cc lavender top blood collection tubes for CBC analysis and two PAXgene blood RNA tubes for RNA isolation. The PAXgene tubes will be stored at -70°C until they are shipped to a Sponsor-designated laboratory for RNA extraction and processing. Blood will also be collected in one 3.5 mL SST collection tube for serum isolation to be used for serum chemistry and 1x 3cc red top blood collection tube for serum isolation to be used for BIO 300 Oral Powder PK analysis. Blood used for serum will be allowed to clot 20-30 minutes and then centrifuged at room temperature for 10-15 minutes. Collected serum will be frozen at -70°C. All blood and serum will be shipped to the sponsor-designated bioanalytical lab for analysis. Additionally, at screening, blood will be collected into another 3.5 mL SST collection tube, and a 3 mL EDTA collection tube to be used for viral testing. Specific blood draw volume requirements for the procedures listed below are detailed in **Section 8.3.1** and **Section 8.3.2**.

Single Ascending Dose

Visit 1 (Screening)

At the screening visit, blood will be collected to acquire the subject's baseline blood counts and serum chemistries, and for viral testing. If a pregnancy test is required for the subject, either a serum or urine test will be done at this time. These test results will assist in determining the subject's ability to be included in the trial (see **Section 5.1 Inclusion Criteria**).

Visit 2 (Day 1)

All subjects will have their blood collected for serum as described above. Serum samples will be collected for pharmacokinetics just prior to and following administration of a single dose of BIO 300 Oral Powder at 30 minutes, 1, 2, 4, 6, 8, and 12 hours. The time of the blood draw will be ± 10 minutes of the nominal time. Subjects will be given a standardized low-soy meal after the 4 h blood draw and 2 h after the 6 h blood draw. Whole blood will be collected as described above for RNA isolation prior to a single dose BIO 300 Oral Powder administration, and at 1, 2 and 4 hours after administration.

Visit 3 (Day 2)

All subjects will have blood serum collected for PK 24 ± 2 hrs after BIO 300 Oral Powder dosing. Whole blood will also be collected for RNA isolation 24 ± 2 hrs after BIO 300 Oral Powder dosing.

Visit 4 (Day 3)

All subjects will have a whole blood and serum collected for CBC, PT/INR, PTT, 48 ± 4 hrs PK and serum chemistry as described above.

Visit 5 (Day 8)

All subjects will have a whole blood and serum collected for CBC, PT/INR, PTT and serum chemistry as described above.

Multiple Single Dose

Visit 1 (Screening)

At the screening visit, blood will be collected to acquire the subject's baseline blood counts, serum chemistries, PT/INR, PPT, and viral testing. If a pregnancy test is required for the subject, either a serum or urine test will be done at this time. These test results will assist in determining the subject's ability to be included in the trial (see **Section 5.1 Inclusion Criteria**).

Visit 2 (Day 1)

All subjects will have their blood collected for serum as described above. Serum samples will be collected for pharmacokinetics just prior to and following administration of a single dose of BIO 300 Oral Powder at 30 minutes, 1, 2 and 4 hours. The time of the blood draw will be ± 10 minutes of the nominal time. Whole blood will be collected as described above for RNA extraction prior to a single dose BIO 300 Oral Powder administration, and at 1, 2 and 4 hours after administration.

Visit 4 (Day 3)

All subjects will have a whole blood and serum collected for CBC, serum chemistry, and PT/INR, PPT as described above.

Visit 5 and 6 (Days 4 and 5)

All volunteers will have their vital signs performed and will be administer a single dose of BIO 300 Oral Powder at the research unit.

Visit 7 (Day 6)

All subjects will have their blood collected for serum as described above. Serum samples will be collected for pharmacokinetics just prior to and following administration of a single dose of BIO 300 Oral Powder at 30 minutes, 1, 2, 4, 6, 8, and 12 hours. The time of the blood draw will be ± 10 minutes of the nominal time. Subjects will be given a standardized low-soy meal after the 4 hr blood draw and 2 hours after the 6-hour blood draw. Serum will also be used for serum chemistry analysis. Whole blood will be collected as described above for RNA extraction prior to a single dose BIO 300 Oral Powder administration, and at 4, 8 and 12 hours after administration. Whole blood will also be collected for CBC analysis.

Visit 8 (Day 7)

All subjects will have blood serum collected for PK 24 ± 2 hrs after BIO 300 Oral Powder dosing. Whole blood will also be collected for RNA extraction 24 ± 2 hrs after BIO 300 Oral Powder dosing.

Visit 9 (Day 8)

All subjects will have blood serum collected for PK 48 ± 4 hrs after BIO 300 Oral Powder dosing.

Visit 10 (Day 13)

All subjects will have a whole blood and serum collected for CBC, serum chemistry, and PT/INR, PPT as described above.

